### **2.5.2 Statistical hypothesis, model, and method of analysis**

The CR at Week 26 will be summarized using point estimate and 2-sided exact binomial 95% ([Clopper-Pearson](#)) confidence intervals.

### **2.5.3 Handling of missing values/censoring/discontinuations**

Subjects who are not evaluable for response at Week 26 for any reason, including missing data and withdrawal from the study before Week 26, will be treated as non-responders in the primary analysis.

### **2.5.4 Supplementary analyses**

The CR will also be derived programmatically using laboratory results (criteria details are stated in the [section 2.5.1](#) ) instead of those reported by the investigators in the response assessment CRF. The response will be derived if two consecutive serial blood count measurements meet the defined requirements, where one of the measurements is done at Week 26. The derived

response will be listed against investigator assessment of response and discrepancies will be identified with justifying comment, when available.

### **2.5.5      Supportive analyses**

Supportive analyses using the CR at Week 26 will be generated per programmatically derived in the following way:

A more stringent definition of CR meeting all the following criteria on 2 consecutive serial blood count measurements at least one week apart:

- Normal hemoglobin concentration for age and gender
- PLT  $>150 \times 10^9/L$
- Absolute neutrophil count (ANC)  $>1.5 \times 10^9/L$

Since this is a more stringent definition of CR, very few CRs will be expected for analysis.

### **Subgroup analyses for the primary endpoint**

The primary efficacy endpoint and supportive analyses (more stringent definition of CR) will be summarized by the above subgroups listed in [section 2.2.1](#) for efficacy. The proportion of the complete response in each subgroup will be summarized using point estimates and 95% exact ([Clopper-Pearson](#)) confidence intervals.

In addition, hematological responses will be listed.

### **2.6      Key secondary endpoint**

Not applicable

### **2.7      Analysis of secondary efficacy objective(s)**

The secondary objectives in this study are:

- To evaluate complete response rate at 3, 12 months and yearly after;
- To evaluate overall response rate at 3, 6, 12 months and yearly after;
- To evaluate duration of response;
- To evaluate overall survival;
- To evaluate the need for transfusion (packed RBC units and platelet units);
- To evaluate the safety and tolerability of eltrombopag in combination with r-ATG and CsA;
- To evaluate clonal evolution;
- To determine the PK of eltrombopag in East-Asian treatment naive SAA patients.

#### **2.7.1      Secondary efficacy endpoints**

##### **CR rate at Week 13, Week 52 and yearly after**

CR rate at specific visit is defined as percentage of subjects who meet the hematological CR criteria by investigator assessment at Week 13, Week 52 and yearly after respectively in FAS. See [Section 2.5.1](#) for definition of CR.

### **Overall response (CR+PR) rate at Week 13, Week 26, Week 52 and yearly after**

Hematologic overall response rate at specific visit is defined as percentage of subjects who achieved hematologic response by investigator assessment at specific visit in FAS.

The overall hematological response is defined as either complete or partial response. CR is defined in [section 2.5.1](#).

Partial response (PR) is defined as blood counts no longer meeting the standard criteria for severe pancytopenia in SAA, equivalent to at least 2 of the 3 criteria below, but are not sufficient for a CR.

- Absolute neutrophil count  $\geq 0.5 \times 10^9/L$
- Platelet count  $\geq 20 \times 10^9/L$
- Reticulocyte count  $\geq 20 \times 10^9/L$

However, improvement in counts that are dependent upon exogenously administered growth factors or transfusion will not be considered as fulfilling response criteria.

The exclusion period of these therapies are detailed below:

- Platelets transfusions: 7 days preceding the assessment of platelet count
- Packed RBC transfusions: 14 days preceding the assessment of hemoglobin
- Growth factors: 21 days preceding the assessment of response.

Of note that the criteria for complete and partial responses must be met on 2 consecutive serial blood count measurements at least one week apart but not more than 4 weeks apart for the Week 13 and Week 26 assessments but only on one blood count measurements for the yearly assessments thereafter.

Patients who relapse or withdraw from the study will be counted and reported as relapsed or withdrawn for all subsequent response assessments. No response (NR) is defined as not fulfilling the response criteria.

### **Time to response**

Time to response is defined as the time from the date of the start of study treatment until the first documented and confirmed response (either CR or PR) per programmatically derived.

Time to complete response is similarly defined as the time from the date of the start of study treatment until the first documented complete response.

All subjects in the FAS will be included in the time to response/CR calculations.

### **Duration of response**

Duration of response will be derived as the time from first documented and confirmed response (either CR or PR) until the time of relapse or death whichever occurs first. Both the responses and the relapse will be programmatically derived. Patients who are neither complete nor partial responders will not be included in the analysis of the duration of response.

Duration of complete response will be similarly derived for patients who had a complete response. Patients who are not complete responders will not be included in the analysis of the duration of complete response.

Clinical relapse is considered as the occurrence of any of the following event in a subject who had achieved a hematological response (CR or PR) but has subsequently lost response (not explained by any other independent concomitant medical conditions) in one blood count measurements:

- meeting again the criteria for SAA, equivalent to patients with at least two of the following parameters in peripheral blood.
  - Absolute neutrophil count  $< 0.5 \times 10^9/L$
  - Platelet count  $< 20 \times 10^9/L$
  - Absolute reticulocyte count  $< 20 \times 10^9/L$
- requirement for transfusion again for subjects who had been transfusion independent
- decrease in any of the peripheral blood counts to: absolute neutrophil count  $< 0.5 \times 10^9/L$  or platelets  $< 20 \times 10^9/L$ .

The analysis of duration of response will be based on response assessment which are derived programmatically using laboratory results instead of those reported in the response assessment CRF.

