8.3 Efficacy

Efficacy assessments include hematologic results, transfusion data, assessment of relapse and survival.

Hematologic parameters will be assessed at Screening, weekly from Week 1 to Week 8, then every 2 weeks to Week 26 (weekly until stabilization of the dose), then every 4 weeks until the end of eltrombopag treatment (every 2 weeks until stabilization of the dose) and yearly during the post-treatment follow-up (up to Year 3). Hematologic parameters will also be assessed as per the investigator decision to assess the maintenance of the response, relapse or for safety reasons.

Transfusion data will be recorded for any transfusion administered during the 60 days prior to treatment start and until the end of eltrombopag treatment for all participants who discontinue eltrombopag due to non-response at W26, relapse or alternative SAA treatment, and until the completion of study follow up for all the other participants. The date and time, content and number of units of each transfusion will be recorded.

Relapse will be determined according to the definition in this section by investigator and will be recorded into eCRF.

All participants will be followed for survival status every 3 months regardless of treatment discontinuation reason up to Year 3 until study completion, death, lost to follow-up, or withdrawal of consent for survival follow-up. Survival information can be obtained via phone, and information will be documented in the source documents and relevant eCRFs.

Hematologic response assessment will be performed by investigators at Week 13, Week 26, Week 52 and yearly after. At Week 13 and Week 26, responses assessment needs to be confirmed by two serial blood count measurements performed 1-3 weeks apart.

Response is defined as blood counts no longer meeting the standard ("Camitta") criteria (Camitta et al 1975) for severe pancytopenia in SAA, equivalent to 2 of the following values (Scheinberg et al 2009).

- Absolute neutrophil count $\geq 0.5 \times 10^9/L$
- Platelet count $\geq 20 \times 10^9/L$
- Reticulocyte count $\geq 20 \times 10^9/L$

A CR will be defined as (all 3 must be met):

- Absolute neutrophil count $> 1.0 \times 10^9/L$
- Platelet count $> 100 \times 10^9/L$
- Hemoglobin $> 100 \text{ g/L}$

A PR will be defined as blood counts that do not meet criteria for SAA but are not sufficient for a CR.

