12.5.1 Efficacy and/or Pharmacodynamic endpoint(s)

For all secondary efficacy endpoints, the FAS will be used.

CR rate at Week 13, Week 52 and yearly after

The number and percentage of participants who meet the hematological CR criteria (at Week 13, Week 52 and yearly after respectively, see [Section 8.3](#) for definition of response) will be presented and 2-sided Exact binomial 95% (Clopper-Pearson) confidence interval will be reported. For missing values and discontinuations, a similar approach will be adopted as for the primary endpoint.

Overall response (CR+PR) rate at Week 13, Week 26, Week 52 and yearly after

Hematologic overall response rate at specific visit is defined as percentage of participants who achieved hematologic response (see [Section 8.3](#)) at specific visit in FAS. The number and percentage of participants who meet the hematological overall response criteria (at Week 13, Week 26, Week 52 and yearly after respectively) will be presented and 2-sided Exact binomial 95% (Clopper-Pearson) confidence interval will be reported. For missing values and discontinuations, a similar approach will be adopted as for the primary endpoint.

Duration of response

For participants who responded, duration of response will be defined as the time from the first date of a response until the first date of relapse or death, which occurs first. Participant still responding at the cut-off date will be censored at date of last response assessment. Only participants with at least 2 response assessments are included in the duration of response, unless they relapsed or died. Duration of response will be estimated using Kaplan-Meier method and will be plotted.

Transfusion-free interval before Week 13 and Week 26

For platelet transfusion, transfusion-free interval is defined as the time from most recent platelet transfusion to the date of response assessment. Only participants with response assessments at specific visits (Week 13 or 26) are included in the transfusion-free interval. Descriptive statistics including mean, SD, median, 25th and 75th quartiles, minimum, and maximum will be summarized for the transfusion-free interval. The same analysis applies to RBC transfusion. The analysis will be presented for participants with CR, PR and NR.

Proportion of participants who becomes transfusion independent

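### Duration of response uses a programmed relapse in place of the investigator's recorded one; two rules are left open or in conflict, and SAP Section 4 does not list the change

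*SAP*

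**What the plan says.** **Protocol.** In 12.5.1, "duration of response will be defined as the time from the first date of a response until the first date of relapse or death". How relapse is established appears only in 8.3: "Relapse will be determined according to the definition in this section by investigator and will be recorded into eCRF". Confirmation by a second count is asked of responses, not relapses: "At Week 13 and Week 26, responses assessment needs to be confirmed by two serial blood count measurements performed 1-3 weeks apart".

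**SAP (primary-analysis and final-analysis versions, same wording).** Section 2.7.1, Duration of response: "Both the responses and the relapse will be programmatically derived", from laboratory results rather than the response CRF. Relapse applies to a responder who "has subsequently lost response (not explained by any other independent concomitant medical conditions) in one blood count measurements", and who meets any one of three criteria:

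1. at least two of ANC <0.5, platelets <20 and reticulocytes <20 (all x10^9/L);
2. renewed need for transfusion after transfusion independence;
3. a decrease of ANC to <0.5 or of platelets to <20.

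Partial response in the same section is "equivalent to at least 2 of the 3 criteria below, but are not sufficient for a CR", using the same three thresholds.

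For complete responders, 2.7.1 says "Duration of complete response will be similarly derived for patients who had a complete response". Section 2.7.3 confines censoring in that analysis to complete responders who have neither changed to PR nor relapsed by the cut-off.

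Section 4 of each SAP, which records changes from the protocol, lists only added endpoints. The document history of the primary-analysis SAP notes that the relapse definition was updated.

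**The concern.** The protocol leaves relapse to a clinician who can judge whether a fall has another explanation and whether response has really been lost. The SAP moves the same wording into a program and does not replace that judgement with a rule. Two competent programmers could therefore produce different Kaplan-Meier curves for a protocol secondary endpoint, and neither curve need agree with the relapses that investigators recorded.

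The investigator's relapse also controls the data. Under protocol 9.1.1, a diagnosis of relapse stops study treatment and ends the efficacy assessments. If the investigator records a relapse that the program does not reproduce, the participant may be censored at the last response assessment, so that a recorded relapse becomes a censoring.

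The primary endpoint is better protected: it stays on investigator assessment, with the programmed CR listed against it (SAP 2.5.1 and 2.5.4). Duration of response has no such pairing.

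**Working it through.** The documents give no numerical target for duration of response, so there is no figure to reproduce. The check compares the rules and enumerates the count patterns.

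**Step 1: source of relapse.** Protocol 8.3: investigator, eCRF. SAP 2.7.1: program. SAP Section 4: not listed. Protocol 12.5.1 does not itself name the source; it is inferred from 8.3, the only place that says how relapse is determined.

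**Step 2: the exclusion.** Laboratory values cannot show whether a fall is explained by a concomitant condition. Adverse events and concomitant therapy are in the eCRF, but the SAP names no data source, reviewer or default.

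**Step 3: is loss of response required first?** Code ANC, platelets and reticulocytes as 1 (at or above the PR threshold) or 0 (below). There are 2^3 = 8 patterns. Four meet the 2-of-3 rule: 111, 110, 101 and 011. The other four (100, 010, 001, 000) are non-response, and all four meet criterion 1. So criterion 1 is exactly the complement of the 2-of-3 rule.

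Take each response pattern to each of the 8 later patterns: 4 x 8 = 32 transitions. The transfusion criterion is left out, and criterion 3 counts only when ANC or platelets cross from 1 to 0.

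| Pattern at response | Relapses by criterion 1 | Added by criterion 3 alone | Total of 8 |
|---|---|---|---|
| 111 | 4 | 2 (to 101, 011) | 6 |
| 110 | 4 | 2 (to 101, 011) | 6 |
| 101 | 4 | 1 (to 011) | 5 |
| 011 | 4 | 1 (to 101) | 5 |

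- Loss of response not required: 6 + 6 + 5 + 5 = 22 of 32.
- Loss of response required: 4 x 4 = 16 of 32, and criterion 3 adds nothing on raw counts.
- Difference: 22 - 16 = 6 transitions, in each of which the later count still meets the 2-of-3 rule and is also a relapse.

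**Step 4: CR to PR.** Let CR start at time a and change to PR at time b.

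| Later course | SAP 2.7.1 (relapse or death) | SAP 2.7.3 (change to PR also ends it) |
|---|---|---|
| No relapse or death; last assessment at c | censored, c - a | event, b - a |
| Relapse or death at d | event, d - a | event, b - a |

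**The case against.** The strongest reply is that the SAP hides nothing. The derivation is set out in 2.7.1, and the history entry dated before database lock records a change to the relapse definition. Protocol 4.1 calls response and relapse objective because they rest on blood counts, and in an open-label single-arm study a programmed rule is a reasonable guard against subjective calls. The disputed wording comes from protocol 8.3. The analysis is descriptive, with no formal test.

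Much of this stands. Programming relapse is legitimate. A single count is also permissible, because the protocol asks for confirmation only of responses at Weeks 13 and 26. What is missing is a record of the departure and rules that a program can follow.

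A reader might go further in four ways, none of which the documents support:

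- *That an unchanged low count in a PR participant is a relapse.* Criterion 3 speaks of a decrease to the threshold, and an unchanged count is not a decrease. Ignoring that word would give 6 x 4 = 24 of 32; the plain text gives 22.
- *That every CR-to-PR participant is censored under one rule and an event under the other.* This holds only for those who never relapse or die. The rest have an event under both rules, at different dates.
- *That the exclusion for concomitant conditions cannot be programmed at all.* The gap is the absence of a stated rule and data source.
- *That investigator relapse is never reported.* Section 2.7.1 carries a relapsed status forward within the investigator-assessed response rates, and 2.7.2 lists response endpoints by both methods. No relapse date by either method is specified.

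**Conclusion.** The point holds. The SAPs change the source of relapse for a protocol secondary endpoint without listing the departure in Section 4. They leave the concomitant-condition exclusion and the role of loss of response open, and their CR-to-PR rules conflict.

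The two readings of loss of response differ in 6 of 32 transitions. That count gives every transition equal weight, uses raw counts and omits transfusions, so it shows that the readings differ but not how often participants would be affected. The documents do not allow the size or net direction of the effect on the Kaplan-Meier estimates to be computed.

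The CR-to-PR conflict concerns only duration of complete response, an analysis added by the SAP; overall duration of response is not touched by it. The primary CR rate at Week 26 is unaffected. The matter merits correction because a protocol endpoint should be reproducible from its text and comparable with the relapses that governed treatment and follow-up.

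**What to change.** - **Add the investigator version.** Analyse duration of response using investigator-recorded relapse in investigator-assessed responders, beside the programmed analysis. Extend the listing in SAP 2.7.2 to show relapse status and date by both methods, with discrepancies marked.
- **Settle CR to PR.** Use one event rule in 2.7.1 and 2.7.3.
- **Complete the programmed rule.** State whether criterion 3 alone is a relapse while the 2-of-3 rule is still met, and how the concomitant-condition exclusion is applied and from which data.
- **Declare it.** List the change of relapse source in Section 4.

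Optionally, add a sensitivity analysis requiring a second low count at least one week later. Unscheduled counts could serve, since "Hematologic parameters will also be assessed as per the investigator decision to assess the maintenance of the response, relapse or for safety reasons"; the text should say how unconfirmed drops at the yearly visits are handled.

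The cost is SAP wording, one derivation from relapse data that the eCRF already collects, and extra columns in a planned listing. The drawback is two duration-of-response results to reconcile in the report.

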### **Transfusion-free interval before Week 13 and Week 26**

For platelet transfusion, transfusion-free interval is defined as the time from most recent platelet transfusion preceding response assessment to the date of response assessment. For RBC transfusion, transfusion-free interval is defined as the time from most recent RBC transfusion preceding response assessment to the date of response assessment.

### **Maximum duration of Platelet and RBC transfusion free**

Transfusion free duration will be defined as the period from the next day after transfusion to the day of the next transfusion. Maximum duration of platelet and RBC transfusion free for each subject will be picked for analysis.

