6.2 Other treatment(s)

6.2.1 Concomitant therapy

All medications (including non-prescription drug and herbal medicines), procedures, and significant non-drug therapies (including physical therapy and blood transfusions) administered after the participant was enrolled into the study (after signing the ICF) must be recorded in the concomitant medications/significant non-drug therapies or procedures pages on the case report forms (CRFs):

- Drug for aplastic anemia other than r-ATG and CsA (G-CSF, iron chelation therapy and supportive therapy except transfusions): from 7 days before the start of administration of the investigational product (or from the screening visit, whichever is earlier) to completion of study;
- RBC and platelet transfusion: from 60 days before the start of administration of the investigational product to the end of eltrombopag treatment for participants who discontinue eltrombopag due to non-response at W26, relapse or alternative SAA treatment, and until the completion of study for all the other participants;
- All concomitant therapy other than the above-mentioned: up to the resolution of the last reported AE.

Transfusions with platelets and/or RBC may be given during study participation as medically necessary per local practice. In general, platelet transfusions should be administered prophylactically when the platelet count $<10 \times 10^9/L$ or when significant bleeding occurs. Prior

to administration of r-ATG, a daily threshold of $20 \times 10^9/\text{L}$ should be used for the duration of the r-ATG course. In participants judged to have additional risk factors for bleeding, a higher prophylactic transfusion threshold of $20 \times 10^9/\text{L}$ is also recommended. Packed RBCs are recommended generally to be administered for hemoglobin $<60 \text{ g/L}$, and it should be individualized according to co-morbidities. Improvement in counts that are dependent upon transfusion will not be considered as fulfilling response criteria in the efficacy assessments (see [Section 8.3](#)).

The use of antibiotics (except for macrolide antibiotics, which may increase the concentration of CsA, mentioned in [Section 6.2.1.1](#)), anti-fungals, and granulocyte colony stimulating factor (G-CSF) are permitted. The local hospital guidelines for treatment of infections / febrile neutropenia should be followed. Cautions should be taken when azole anti-fungals are administered, mentioned in [Section 6.2.1.1](#).

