## **General analysis conventions**

**Pooling of centers:** Unless specified otherwise, data from all study centers will be pooled for the analysis. Due to expected small number of patients enrolled at centers, no center effect will be assessed.

**Qualitative data** (e.g., gender, race, etc.) will be summarized by means of contingency tables; a missing category will be included as applicable. Percentages will be calculated using the number of patients in the relevant population or subgroup as the denominator.

**Quantitative data** (e.g., age, body weight, etc.) will be summarized by appropriate descriptive statistics (i.e. mean, standard deviation, median, minimum, and maximum and first and third quartiles when appropriate). PK parameters except Tmax will be summarized by appropriate descriptive statistics (n, arithmetic mean, CV% mean, standard deviation (SD), median, geometric mean, CV% geo-mean, minimum and maximum).

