### **Proportion of subjects who become transfusion independent**

The number and percentage of subjects with platelet or RBC transfusion independence during the study will be presented respectively. This analysis will be performed for the subgroup of subjects with baseline transfusion dependence.

Post-baseline transfusion independence is defined as follows:

- Platelet transfusion independence: The subjects who are transfusion dependent at baseline become transfusion free for a period of at least 4 weeks after baseline.
- RBC transfusion independence: The subjects who are transfusion dependent at baseline become transfusion free for a period of at least 8 weeks after baseline.

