### **Maximum duration of Platelet and RBC transfusion free**

Maximum duration of platelet and RBC transfusion free will be summarized by descriptive statistics including mean, SD, median, 25th and 75th percentiles, minimum, and maximum separately.

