### **Maximum duration of Platelet and RBC transfusion free**

This analysis will be only performed for the subgroup of subjects with baseline transfusion dependent.

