### **2.7 Analysis of secondary efficacy objective(s)**

The secondary objectives in this study are:

- To evaluate complete response rate at 3, 12 months and yearly after;
- To evaluate overall response rate at 3, 6, 12 months and yearly after;
- To evaluate duration of response;
- To evaluate overall survival;
- To evaluate the need for transfusion (packed RBC units and platelet units);
- To evaluate the safety and tolerability of eltrombopag in combination with r-ATG and CsA;
- To evaluate clonal evolution;
- To determine the PK of eltrombopag in East-Asian treatment naive SAA patients.

All analysis will not be reproduced in final analysis for secondary endpoints which are at or prior to Week 26. These include CR rate at Week 13, overall response (CR+PR) rate at Week 13 and Week 26, time to response, transfusion-free interval at Week 13 and Week 26, transfusion frequency and amount at Week 13 and Week 26, changes in platelet count, hemoglobin and neutrophil count at Week 13 and Week 26.

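### Maximum transfusion-free duration has no end point for the interval after the last transfusion, so participants who stop being transfused can be under-scored

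*SAP*

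**What the plan says.** SAP 2.7.1, in both the primary-analysis and the final-analysis version, defines the quantity in one sentence: "Transfusion free duration will be defined as the period from the next day after transfusion to the day of the next transfusion". Each participant's largest value is then analysed.

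The method in SAP 2.7.2 is plain summary statistics: "Maximum duration of platelet and RBC transfusion free will be summarized by descriptive statistics including mean, SD, median", with quartiles and range. The handling rule in SAP 2.7.3 concerns only who is analysed: "This analysis will be only performed for the subgroup of subjects with baseline transfusion dependent". Section 4 of both versions lists the endpoint among those added beyond the protocol and defines it no further.

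Two neighbouring transfusion outputs do not need a later transfusion:
- For the Week 13 and Week 26 output, the "transfusion-free interval is defined as the time from most recent platelet transfusion preceding response assessment to the date of response assessment", so it closes at an assessment date.
- Platelet independence requires that baseline-dependent participants "become transfusion free for a period of at least 4 weeks after baseline"; the RBC version uses 8 weeks.

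Final-analysis SAP 2.7 lists what will not be produced again, including "time to response, transfusion-free interval at Week 13 and Week 26".

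**The concern.** The best outcome for this endpoint is that a participant stops needing transfusions. That outcome leaves the final interval without a closing transfusion, and the definition gives it no other end. A rule that counts only closed intervals therefore omits the stretch that matters most for these participants, and it rewards a late extra transfusion because that transfusion closes a long gap. The same report could call a participant platelet transfusion independent and show a maximum transfusion-free duration shorter than the 4 weeks that independence requires.

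Need for transfusion is a secondary objective, and Protocol 4.5 names reduced need as an expected benefit. At the final analysis the Week 13 and Week 26 intervals are dropped, while follow-up to Year 3 makes the unclosed interval potentially very long.

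**Working it through.** The documents give no figure for this endpoint, so there is none to reproduce. The histories below are assumed, to show how the rule behaves; they are not trial data.

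**Inputs.** The definition comes from SAP 2.7.1. Day 183 (Week 26) and Day 1093 (Year 3) come from Protocol Table 8-1. Closing at Day 1093 assumes that transfusion data are still being collected for that participant.

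**Formulas.**
- Closed interval between transfusions on days a and b, both end days counted: b − (a + 1) + 1 = b − a.
- Last interval, with last transfusion on day L and closing day E: E − L.
- Understatement, with G the longest closed gap: (E − L) − G when positive, otherwise 0.

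| Assumed transfusion days | As written | Last interval closed at Day 183 |
|---|---|---|
| 3, 10, …, 45, then none | 7 | 183 − 45 = 138 |
| The same, plus Day 150 | 150 − 45 = 105 | larger of 105 and 183 − 150 = 33, so 105 |
| 3, 10, …, 178 | 7 | larger of 7 and 183 − 178 = 5, so 7 |
| 5, 15, 30, 45, 60, then none | 15 | 183 − 60 = 123 |
| 5, 15, 30, 55, 70, then every 14 days to 182 | 25 | larger of 25 and 183 − 182 = 1, so 25 |

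**What the table shows.**
- Row 1 is understated by 138 − 7 = 131 days at Day 183. At Day 1093 the last interval is 1,093 − 45 = 1,048 days and the written score is still 7.
- Rows 1 and 3 tie at 7 as written, although one participant stopped at Day 45 and the other continued to Day 178.
- From row 1 to row 2, an extra transfusion raises the written score from 7 to 105. With the last interval closed it lowers the score from 138 to 105, the expected direction.
- Rows 4 and 5 are in the wrong order as written (15 against 25) and in the right order once closed (123 against 25).

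**Check against independence.** The row 1 participant is transfusion free for 138 days, which meets 4 × 7 = 28 days, but the written maximum is 7. For RBC transfusions on Days 3, 17, 31, 45 and 59, the last interval is 183 − 59 = 124 days, against a threshold of 8 × 7 = 56, while the written maximum is 14.

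**Few or no post-baseline transfusions.** The SAP does not say whether a transfusion before Day 1 can start an interval. Everyone analysed is baseline dependent, so by Protocol 8.2 has at least one transfusion in the 4 weeks (platelets) or 60 days (RBC) before Day 1. Take a single post-baseline platelet transfusion on Day 3. If earlier transfusions count, the interval it closes runs from a transfusion somewhere between Day −28 and Day −1. There is no Day 0 in the SAP's study-day rule, so its length is between 1 + 2 = 3 and 28 + 2 = 30 days. If earlier transfusions do not count, there is no closed interval. Either way, the 183 − 3 = 180 days after Day 3 are left out.

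**Search for a closing rule elsewhere.** The general data rule in SAP 2.1 treats events without an end date as ongoing and does not impute one. Time to response, duration of response and overall survival each have their own censoring date in SAP 2.7.3; this endpoint has none.

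**The case against.** The strongest reply is that the SAP is silent on the last interval rather than excluding it. The independence definition uses the term transfusion free for periods that need no closing transfusion, so a programmer could reasonably include the final stretch. It stands that no sentence expressly removes that interval. But the definition gives one end point only, and a programmer who adds another must choose a date that the SAP does not supply.

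The second reply is that little depends on this. The trial is single-arm with no formal test, the endpoint was added for support, no ranking of participants is planned, and the error makes results look worse. All of that stands and limits the weight of the point. The independence proportion also remains at the final analysis, as do transfusion frequency, amount and decrease at Week 52 and yearly, but none of these measures length.

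Two stronger readings are tempting and are not supported:
- A reader might infer that participants with one or no post-baseline transfusion have no value at all. The restriction to baseline-dependent participants means each has a recorded earlier transfusion, which may start an interval, so a missing value is not established.
- A reader might also infer that, once transfusion collection has stopped, the 4- and 8-week windows of the other outputs would be scored as transfusion free. The SAP nowhere reads absent records that way, and its general conventions for qualitative data say that "a missing category will be included as applicable".

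**Conclusion.** The concern holds as a defect in one definition. Followed as written, SAP 2.7.1 omits the interval after the last transfusion. It under-scores any participant for whom that interval is longer than every earlier gap, which is the usual case for someone who stops transfusions but not a universal one. In the illustrations the understatement at Day 183 is 131 days for weekly transfusions ending on Day 45, and 123 − 15 = 108 days for the history ending on Day 60. These figures rest on assumed histories; the effect on the reported mean or median depends on transfusion records that the documents do not give.

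The defect affects an added descriptive endpoint and understates benefit. It should not be read as casting doubt on the primary endpoint, nor on the Week 13 and Week 26 interval or the independence proportion, which have their own definitions. It matters most at the final analysis, where nothing else reports how long participants went without transfusion.

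**What to change.** In SAP 2.7.1 of both versions:

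1. State that the interval after the last transfusion is included in the maximum and ends at the earliest of the end of transfusion data collection, death, withdrawal of consent and data cut-off. The end of collection is already defined: Protocol 6.2.1 runs it "to the end of eltrombopag treatment for participants who discontinue eltrombopag due to non-response at W26, relapse or alternative SAA treatment", and to study completion for everyone else; Protocol 8.3 agrees.
2. State whether the first interval begins at Day 1 or may begin at an earlier transfusion. Day 1 is suggested, because it gives every analysed participant a value: at Day 183, 180 days for a single transfusion on Day 3 and 183 days for none.
3. Flag each maximum that comes from an open interval, report the number of such values beside the summary statistics, and footnote that they are lower bounds that depend on length of follow-up. That length differs by reason for stopping eltrombopag.

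The cost is SAP wording, a small programming change and a table footnote. No new data are needed.
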